## **5.6 3, 6 and 12 month assessments**

Outcome assessments will be performed via structured and scripted telephone interviews. Average pain and itch (0-10 NRS), frequency of pain and itch during the past 24 hours at the patient's donor site, as well as average pain and itch (0-10 NRS) and frequency of pain and itch during the past 24 hours at the patient's graft site will be assessed. The presence of neuropathic pain symptoms (DN4, S-LANSS) will also be assessed, as well as pain and itch related interference in daily activities (Brief Pain/Itch Inventory Interference Subscales). Information regarding current medication use (both standing and PRN) and health services utilization (including burn care such as PT, OT) will also be obtained. At these time points the following assessments will also be administered: The frequency of scratching and its effect on itch related to the burn, at either the donor site or the graft site, will be evaluated. The location (Regional Pain Scale) and intensity (0-10 NRS) of pain and itch symptoms (using a modified RPS) in any locations other than the donor and graft sites will be assessed, along with the presence and severity of other somatic symptoms (e.g. headache, dizziness, and itching). General health (SF-12), depressive and anxiety symptoms (DASS), and PTSD symptoms (PSS-I) will be assessed. Sleep quality will be assessed using the MOS Sleep Scale. Global recovery after burn injury will be evaluated using a 0-100 percent improvement scale (0% =no recovery, 100% =completely recovered). Pending litigation or workman's compensation claims related to the burn injury will also be evaluated (at month 12). Alcohol abuse is common among injured patients, and increased alcohol or drug use after trauma is likely to be related to chronic pain and itch outcomes. Quantity and frequency of alcohol and drug use will be assessed at the 24 week and 48 week follow-up time points, using questions from the TWEAK and Substance Abuse Outcomes Module. Photos of both the graft site and donor site (if present) will be obtained using a standard algorithm using any available digital camera/smartphone and stored on the research database. If patients do not have access to a digital camera one will be mailed to their address with a return label, or they will have the photos taken during a follow-up clinic visit. We will also collect information about the number of servings of fish, olive oil, and any Vitamin D or fish oil supplements that have been consumed since the 6 week treatment period. Participants will be contacted at 9 months for a brief participant contact information update. This will ensure that the participant's address, phone number, and e-mail address are up-to-date for study contact purposes.

## **6 Statistical Plan**

### **6.1 Sample Size Determination**

The purpose of this study is to assess study feasibility, safety and to obtain initial effect size estimates and confidence intervals to use in sample size calculations for a larger study. Previous studies of Vitamin D and n-3 PUFAs for the treatment of chronic pain are poorly generalizable to this setting because 1) they examine treatment of established chronic pain states versus developing pain states, 2) do not involve trauma exposure/acute stress, and 3) are not preventive studies. Therefore, this pilot study will be instrumental in demonstrating feasibility and safety of the protocol, and estimates of efficacy along with confidence intervals will be helpful for planning a larger follow-up study.

**Justification for the sample size.** We will target 15 individuals in each group (60 total) so that feasibility and safety may be determined as well as provide potential evidence for efficacy. Below, calculations are provided to justify sample size for each objective.

**Feasibility:** Assuming that observed follow-up will be around 80%, this study will allow us to estimate follow-up rates to within  $\pm 10\%$  with a 95% confidence interval given we reach the enrollment target of 60. Allowing for up to 20% loss, with 30 participants treated in each n-3 PUFA arm of our study, our study is powered at 90% to detect a difference of 2.6% of DHA (an n-3 PUFA) in total fatty acid content considering a standard deviation of 1.3%. This study (30 per Vitamin D arm) is powered at 83% to detect a change of 9 ng/dl in Vitamin D level assuming a SD of 10.5.

**Efficacy:** Allowing for up to 20% loss and assuming a common standard deviation of 2.6 (approximated from our pilot dataset) and no interaction between treatments, randomizing 30 participants to each comparison group (Vitamin D/n-3 PUFA versus control) will allow us to estimate the difference in mean pain severity to within  $\pm 1.4$  using a two-sided 95% confidence interval.

## 6.2 Statistical Methods

### Primary outcome assessments and analysis:

**Feasibility:** The primary objective of this pilot study is to ensure that we are able to enroll participants and make follow-up assessments. The subsequent study will be considered feasible if we are able to collect follow-up assessments on >80% of enrolled participants at 6 weeks following MThBI, and >80% of participants at 1 year. Medication adherence will be assessed by pill counts at the end of the study and quantitative determination of plasma fatty acid/Vitamin D concentration. The subsequent study will be considered feasible if at least 75% of participants take at least 80% of their assigned medication (per pill count) and there is a statistically significant increase in Vitamin D and fatty acid concentration in treated individuals versus controls. T-tests will be used and a  $p < 0.05$  will be considered statistically significant.

**Safety:** Another main objective of this pilot study is to ensure safety of both treatments as well as combined. To determine safety, we will tabulate the number of serious adverse events in each treatment arm and perform a descriptive review of adverse events in the study, and make a determination about the degree of relatedness of each adverse event with the intervention using CTCAE criteria outlined in Appendix 2. The recorded adverse events in each arm will be tabulated descriptively, but no inferential statistics (p-values and confidence intervals) for comparing arms will be reported.

**Efficacy:** Estimates of efficacy will be obtained via repeated measures analysis using mixed effects models (PROC MIXED in SAS 9.4). Prior to unblinding the data, our study statistician will perform a blind review of the data in which statistical models will be developed and tested using dummy (computer generated) treatment assignments. The goal of this is to fit the most appropriate model given aggregate data. Graft site pain severity will be collected in four waves across time; therefore, we will use mixed effects modeling with random error using an unstructured covariance matrix. The model will include fixed effects for PUFA, Vitamin D, their interaction, time, and the interactions between groups and time, as well as fixed effects for site, gender, and race/ethnicity. During blind review, competing nested fixed effect models will be compared. We will consider modeling time using either a) time as continuous variable with a linear model (i.e., slopes only), b) time as a continuous variable with a higher order polynomial model (up to cubic, given 4 time points), or c) time as a class variable. Competing fixed effect models will be fitted using maximum likelihood and compared using the BIC criterion. Once the form for the fixed effect model is selected, the final model will be fit using restricted maximum likelihood. After unblinding the data, we will use appropriately specified linear contrasts of the model parameters to estimate mean differences across groups at each time point along with 95% confidence intervals.

**Interim analysis:** Two interim analyses are planned after the enrollment of the 20th and 40th patients in the study. This will be conducted to ensure safety, perform a feasibility assessment, and assess potential efficacy. This optimizes study ethics, as it ensures safety of current and future study participants, allows

optimization of study protocol based on results of safety and feasibility assessment, and allows an efficacy assessment with appropriate statistical “penalty” for an interim look. Adverse events will be qualitatively reviewed at two interim analyses occurring after enrollment of the 20th patient and after enrollment of the 40th patient. While study investigators, staff, and participants remain blinded, the study statistician will prepare a qualitative summary of adverse events by type over the treatment groups. The results will be reported to investigators in aggregate such that blinding is maintained.

Significance thresholds for interim analyses for potential efficacy will be adjusted using the O’Brien-Fleming approach. In order for the trial to stop enrolling because efficacy (superiority) is established after the first interim analysis (after 20 patients enrolled), the boundary critical value of 3.428 and corresponding alpha of 0.0006 must be reached. In order for the trial to stop enrolling because efficacy is established after the second interim analysis (after 40 patients enrolled), the boundary critical value of 2.431 and corresponding alpha of 0.0151 must be crossed. After the final analysis (third analysis) a critical value of 1.985 and a p-value of 0.0471 will be used. This final, adjusted p-value threshold of 0.0471, allows for a statistical “penalty” to be assessed because of the interim look. Given that this is a pilot study, we believe it is critically important to assess our safety, feasibility and potential efficacy outcomes at interim analysis.

Given that the study was terminated early after enrollment of the 24th patient after one interim analysis, the final, adjusted p-value threshold of 0.0492, allows for a statistical “penalty” to be assessed because of the interim look.

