### **3.3 Primary Study Endpoints**

The primary endpoint of this study will examine the safety, feasibility and efficacy of n-3 PUFAs/Vitamin D to improve chronic pain outcomes following major thermal burn injury. **Outcome to assess safety:** Safety outcomes will be met after descriptive review of adverse outcomes, and comparison of adverse events is made across treatment groups by investigative team at the conclusion of the study. **Outcome to assess feasibility:** 60 patients will be enrolled, randomized into one of 4 treatment arms in a 1:1:1:1 ratio, and treated with study drug for 6 weeks following Major Thermal Burn injury severe enough to warrant surgery within a 24 month period. Proportion of participants completing following up at 6 weeks will be reported. The concentration of Vitamin D and n-3 PUFAs will be calculated before and after the 6 week treatment in each treatment arm to assess the response (expect an increase in both Vitamin D and n-3 PUFA in treatment arms). **Outcome to assess efficacy:** Efficacy of Vitamin D/PUFA will be measured by difference in pain severity in treatment arms versus control arms. We will 1) calculate a model estimated mean of chronic pain severity and corresponding 95% Confidence interval in each study group and 2) determine the slope of pain recovery among individuals treated with Vitamin D and n-3 PUFAs relative to control participants using a linear mixed model adjusting for sex, ethnicity, and study site.

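### The Section 6.2 feasibility rule omits the Section 3.3 recruitment outcome, so a trial ended at 24 of 60 can pass it; its vitamin D condition has only about 37-52% power at that size

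*Combined protocol and SAP*

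**What the plan says.** Section 2 makes feasibility, with safety, the primary objective. Section 3.3 begins the feasibility outcome with recruitment: "60 patients will be enrolled, randomized into one of 4 treatment arms in a 1:1:1:1 ratio", treated for 6 weeks after a burn "severe enough to warrant surgery within a 24 month period". It then lists 6-week follow-up and biomarker response: "The concentration of Vitamin D and n-3 PUFAs will be calculated before and after the 6 week treatment in each treatment arm".

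Section 6.2 opens its feasibility paragraph with "The primary objective of this pilot study is to ensure that we are able to enroll participants and make follow-up assessments". Two sentences then say when the larger study counts as feasible. The first begins "The subsequent study will be considered feasible if we are able to collect follow-up assessments on >80% of enrolled participants at 6 weeks" and adds more than 80% at 1 year. The second asks that at least 75% of participants take at least 80% of their medication by pill count, and that "there is a statistically significant increase in Vitamin D and fatty acid concentration in treated individuals versus controls", judged by t-tests at p<0.05. How the two sentences combine is not stated.

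Section 6.1 supports the biomarker conditions with two power statements. For vitamin D: "This study (30 per Vitamin D arm) is powered at 83% to detect a change of 9 ng/dl in Vitamin D level", with an SD of 10.5. For fatty acids, after 20% loss from 30 per arm: "our study is powered at 90% to detect a difference of 2.6% of DHA", with an SD of 1.3%.

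At the end of its interim-analysis text, Section 6.2 records early termination after the 24th patient and resets the final p-value threshold to 0.0492. The feasibility rule and the Section 6.1 figures are not revisited.

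**The concern.** The rule in Section 6.2 settles a primary objective, and Section 2 intends the data for designing a large trial. Section 6.2 names enrolment as part of what the pilot must show and then never tests it. Every condition is either a percentage of those enrolled or a significance test, so none depends directly on how many patients were recruited or how fast. A favourable verdict could be reached and passed on to the larger trial without mention of the 24 of 60.

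The small size also pulls the other way. Because a significant vitamin D difference is itself a condition, the loss of sample makes that condition easy to fail even if supplementation works as planned. The rule is then too lenient on recruitment and, on vitamin D, likely to fail for lack of patients.

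**Working it through.** **1. Recruitment, set side by side**

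| Element | Feasibility outcome in 3.3 | Condition in the 6.2 rule |
|---|---|---|
| 60 enrolled and treated in 24 months | Yes | None |
| Follow-up at 6 weeks | Yes, proportion reported | >80% |
| Follow-up at 1 year | Not listed | >80% |
| Pill count | Not listed | ≥75% of participants taking ≥80% |
| Vitamin D and fatty acid levels | Yes | Significant t-tests |

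Enrolment reached 24/60 = 40%. The smallest passing counts at 24 are:
- Follow-up: 0.80 × 24 = 19.2, so 20 of 24 (83%, exact 95% CI 63% to 95%).
- Adherence: 0.75 × 24 = 18 of 24.

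With these counts (20 of 24 at both visits) and significant biomarker tests, every stated condition is met.

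The 3.3 target implies 60/24 = 2.5 patients per month. At that pace 24 patients take 24/2.5 = 9.6 months. Without the length of enrolment, one cannot say whether the trial was ahead of or behind pace.

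**2. Vitamin D power**

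Inputs from Section 6.1: difference 9, SD 10.5 (units as printed), 30 per side, 20% loss. The loss is written in the DHA sentence, but the vitamin D figure reproduces only if it applies there too: 30 × 0.8 = 24. Alpha is 0.05 (Section 6.2), and a two-sided test is assumed.

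Method: two-sample t-test with noncentrality 9 / (10.5 × √(1/n₁ + 1/n₂)) and n₁ + n₂ − 2 degrees of freedom. The 95% CI half-width is t(0.975) × 10.5 × √(1/n₁ + 1/n₂).

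Plan's figure: at 24 v 24 the noncentrality is 9 / (10.5 × √(2/24)) = 2.97 and power is 82.8%, matching the stated 83%. With no loss (30 v 30) it would be 90.4%. A one-sided test at 24 v 24 gives 90.0%, so two-sided is the reading that fits.

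| Analysed per side | Power | 95% CI half-width |
|---|---|---|
| 24 v 24 (plan) | 82.8% | 6.1 |
| 12 v 12 (24 enrolled, no loss) | 51.9% | 8.9 |
| 10 v 10 | 44.2% | 9.9 |
| 9 v 9 | 40.1% | 10.5 |
| 6 v 13 (uneven, about 20% loss) | 37.4% | 10.9 |

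Nine to ten per side is about 20% loss from 12. At these sizes the half-width is about as large as the planned difference of 9, and a true difference of 9 would miss p<0.05 in about 48% to 63% of trials.

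**3. DHA power**

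Standardised difference 2.6/1.3 = 2. At 24 v 24 the noncentrality is 2 / √(2/24) = 6.93 and power exceeds 99.9%. The stated 90% does not follow from the printed inputs. At those inputs power is still 99.7% at 12 per side and 97.8% at 9.

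**4. Follow-up precision**

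Half-width 1.96 × √(0.8 × 0.2 / n): ±10.1 points at n = 60, matching the plan's ±10%, and ±16.0 points at n = 24.

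**The case against.** The strongest reply is that the plan does not ignore recruitment. Section 3.3 states the target among the primary endpoints, Section 3.8 keeps records of screened, excluded and refusing patients, and the interim analyses in Section 6.2 include a feasibility assessment. A team following the whole document would report 24 of 60 anyway. That stands as far as reporting goes. But the only rule that turns results into a verdict is in Section 6.2, and it does not say whether missing the target matters.

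A reader might infer that recruitment failed. The documents do not support this. They give no reason for termination; Section 6.2 allows an efficacy stop and Section 7.5 allows stopping for medical, safety, regulatory or other reasons. A trial on pace at 2.5 per month could have been stopped for something unrelated to recruitment, so a verdict on the count alone would be unfair.

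A reader might also infer that the DHA condition is underpowered at this size, by trusting the stated 90%. That figure conflicts with its own inputs and the documents do not show which is wrong, so no reduced DHA power can be derived from it.

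It is fair to add that this is a pilot with enrolment closed, so power can no longer change the design, and that Section 6.1 conditions its follow-up precision on reaching 60. But the plan makes p<0.05 a feasibility condition, so power still governs how a null result is read.

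**Conclusion.** The concern holds. The Section 6.2 rule leaves out the recruitment outcome set in Section 3.3, and a trial ended at 40% of target can be called feasible under it. This is a gap in the rule. It is not evidence that recruitment failed or that a wrong verdict was issued.

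The vitamin D condition falls from 83% power as planned to about 40-52% with an even split of the 24 patients, and to 37% in the uneven case examined. This assumes the plan's difference and SD, a two-sided test, and 9 to 12 analysed per side; the actual split and losses are not given. A non-significant vitamin D result at this size is weak evidence of infeasibility.

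The mismatch between the stated 90% DHA power and its inputs is a separate error that neither conclusion depends on.

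**What to change.** 1. Carry the 3.3 recruitment outcome into the 6.2 feasibility conclusion. Report 24/60, the length of enrolment, the monthly rate against 2.5 per month, and the reason for termination. Do not conclude that recruitment was feasible unless the rate was on pace with the 3.3 target and enrolment stopped for a reason unrelated to recruitment. Label this as added after termination, and state that all 6.2 conditions must be met.
2. Keep the prespecified t-tests as the deciding tests and report each biomarker difference with its 95% CI. If vitamin D has p≥0.05 but the interval includes 9 units, record the condition as not met and state that the planned difference is not excluded.
3. Beside the Section 6.1 figures, state that at 24 enrolled vitamin D power is about 37-52% and follow-up precision about ±16 points. Correct the 90% DHA power or its inputs so that they agree.

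The cost is SAP wording and a few reported intervals; no new data are needed. There are three downsides. The feasibility conclusion may become less favourable. The recruitment judgement is made with 24/60 already known, which is why it should be tied to the existing target and labelled. And item 2 improves interpretation only: it does not restore the lost power.

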## **4.3 Method for Assigning Subjects to Treatment Groups**

Once a potential subject has been successfully screened, does not meet any exclusion criteria, is willing to participate in the study, and signs informed consent, the patient will be randomized by the study site using a block randomization scheme with permuted block sizes stratified on ethnicity and sex. A randomization table will be generated by the study statistician and placed in the randomization module in RedCap. Only the investigational pharmacy and study statistician will be unblinded to the drug the patient is receiving. They will not reveal this to the patient care team, investigative team, or to the patient. Identical dosing schedule, route of administration, number of pills in each dose, and the appearance of the capsules will be identical among each group. At the time of patient discharge from the study site, the study site (nursing staff) will dispense a supply of study medication for the patient to complete a 6 week course (this medication was initially dispensed to the patient from IDS at the time of enrollment). Only the IDS will know the identity of each group's treatment, as well as the study statistician. This will only be provided to the study statistician at the end of the study.

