## **4.5 Subject Compliance Monitoring**

Administration of the study drug will be completed by burn center nursing staff and will be documented in the medication administration record (MAR). Reasons for refusal will be documented in the MAR. Following the treatment period, patients will receive weekly surveys delivered by text message/e-mail via RedCap or by phone call that will assess the number of missed doses as well as a graft-site pain rating (0-10 NRS). In addition, a biological test for medication compliance will be performed by comparing starting concentration of n-3 PUFAs/Vitamin D to ending concentration (e.g. an increase in PUFA level is an additional marker of compliance).

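### The biomarker feasibility test is an unadjusted t-test with no named response; baseline-adjusted ANCOVA would usually give the vitamin D half more power from the same samples

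*Combined protocol and SAP*

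**What the plan says.** Section 6.2 (Feasibility) counts the follow-on study as feasible only if, among other conditions, "there is a statistically significant increase in Vitamin D and fatty acid concentration in treated individuals versus controls". The next sentence begins "T-tests will be used and a" and gives 0.05 as the significance level. It names no response variable, covariate or sidedness.

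Other sections bear on what is being tested:

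- Section 3.3: "The concentration of Vitamin D and n-3 PUFAs will be calculated before and after the 6 week treatment in each treatment arm".
- Section 4.5 describes a biological compliance check, "comparing starting concentration of n-3 PUFAs/Vitamin D to ending concentration".
- Section 6.1 describes the study as "powered at 83% to detect a change of 9 ng/dl in Vitamin D level assuming a SD of 10.5", with 30 participants per vitamin D comparison group. The 20% loss allowance is written in the preceding DHA sentence: "Allowing for up to 20% loss, with 30 participants treated in each n-3 PUFA arm of our study".
- Section 4.3 randomizes with "permuted block sizes stratified on ethnicity and sex".

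No section plans a baseline-adjusted analysis of the biomarkers. The mixed model for pain in 6.2, by contrast, adjusts for site, gender and race/ethnicity.

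**The concern.** The criterion turns on whether p falls below 0.05, and two quite different t-tests fit the text. A t-test on the 6-week level makes no use of the baseline. A t-test on change subtracts the whole baseline, which adds noise when baseline and follow-up correlate below 0.5. The two can disagree on the same data, and the plan does not say which decides. ANCOVA weights the baseline by its observed relation to the 6-week level. Except near zero correlation, its power is essentially at least that of the better of the two.

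At stake is an avoidable false negative on the vitamin D half of the exposure criterion: a supplement that raises levels as assumed but fails the test. The risk grows at small numbers, and section 6.2 records termination after the 24th patient.

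**Working it through.** **Inputs.** From 6.1: vitamin D difference 9, SD 10.5, 30 per comparison group, 20% loss, hence 30 × 0.8 = 24 per group. From 6.2: alpha 0.05 and 24 patients enrolled, hence about 12 v 12 per factor with no loss, or about 10 v 10 with 20% loss (12 × 0.8 = 9.6). The baseline/6-week correlation r is not in the documents; 0.3, 0.5 and 0.7 are assumed. Section 6.1 does not say whether 10.5 is the SD of a level or of a change, so both are shown.

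**Reproducing the plan's figure.** For a two-sample t-test, noncentrality = 9 / (10.5 × √(2/24)) = 9 / 3.03 = 2.97, with two-sided critical value 2.013 on 46 df. Power is 82.8%, matching the stated 83%. A one-sided test at 24 per group gives 90.0%, and a two-sided test at 30 per group gives 90.4%. The stated figure is therefore a two-sided, unadjusted t-test with the loss allowance applied.

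**Reading A: 10.5 is the SD of a level.**

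- Change-score SD = 10.5 × √(2(1 − r)) = 12.42, 10.50, 8.13 at r = 0.3, 0.5, 0.7.
- ANCOVA residual SD = 10.5 × √(1 − r²) = 10.02, 9.09, 7.50.

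| Power, reading A | r = 0.3 | r = 0.5 | r = 0.7 |
|---|---|---|---|
| 24 v 24, t-test on level | 83% | 83% | 83% |
| 24 v 24, t-test on change | 69% | 83% | 96% |
| 24 v 24, ANCOVA (baseline, both factors) | 85% | 91% | 98% |
| 12 v 12, t-test on level | 52% | 52% | 52% |
| 12 v 12, t-test on change | 40% | 52% | 74% |
| 12 v 12, ANCOVA (baseline, both factors) | 54% | 62% | 78% |

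The t-test rows use the noncentral t. The ANCOVA rows are simulated. The closed form with one df lost gives slightly more (86.1, 91.8, 98.2% at 24 v 24; 55.6, 63.8, 80.0% at 12 v 12) because it ignores chance baseline imbalance. At 10 v 10 the level t-test has 44%, and ANCOVA on baseline alone has about 46%, 53% and 69% (simulated).

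**Reading B: 10.5 is the SD of the change.** The implied level SD is 10.5 / √(2(1 − r)) = 8.87, 10.50, 13.56, and the ANCOVA residual SD is 8.47, 9.09, 9.68. At 24 v 24 the change t-test has 83%, the level t-test 93%, 83% and 61%, and ANCOVA 95%, 92% and 88% (closed form).

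**Zero correlation.** Under reading A, simulated ANCOVA on baseline has 81.7% at 24 v 24, 50.0% at 12 v 12 and 41.9% at 10 v 10. The level t-test has 82.8%, 51.9% and 44.2%. ANCOVA loses about 1 to 3 points.

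**DHA.** Section 6.1 gives a difference of 2.6 and SD 1.3, so d = 2.6 / 1.3 = 2. Taking 1.3 as the SD of the response tested, the t-test has about 100% power at 24 v 24, 99.7% at 12 v 12 and 98.8% at 10 v 10. (The plan states 90%; its own inputs give more. That is a separate matter.)

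**Adding the strata.** At 12 v 12, with sex and race/ethnicity added as terms that do not predict the level, simulated power is about 49%, 56% and 74%. Without them it is 54%, 62% and 78%. The cost is 5, 6 and 4 points, and at r = 0.3 the larger model falls below the level t-test (52%).

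**The case against.** A reader might infer that the plan ignores the baseline. The documents do not support that. Section 6.2 speaks of an increase, 3.3 of levels before and after treatment, 4.5 of starting against ending concentration, and 6.1 of a change of 9. These fit a t-test on change, which uses the baseline, at least as well as one on levels. What stands is that the response is not named and ANCOVA is not planned.

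A reader might also infer that the whole exposure criterion is short of power, or that a failed biomarker test alone would sink feasibility. On the plan's inputs the DHA half has nothing to gain. The biomarker is one condition beside follow-up above 80% and pill-count adherence. Section 3.3 also sets 60 patients enrolled within 24 months, and the trial stopped at 24, so that target was missed whichever biomarker test is used.

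The other objections are fair. The t-test is valid under randomization and agrees with the plan's own power statement. The size of the gain rests on a correlation the documents do not supply. Section 1.1 reports vitamin D insufficiency in about 76% of the U.S. population and 97% of African Americans, which suggests that baseline levels differ between participants but does not fix a value for r. Covariates are not free at this size. Replacing a prespecified test after termination, when interim looks included feasibility, would need justification.

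**Conclusion.** The point holds as an efficiency and specification improvement to a valid analysis. It applies to vitamin D only. Under either reading of the SD, ANCOVA on baseline is at least as powerful as either t-test unless the correlation is near zero, where it may lose 1 to 3 points.

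Under reading A, the gain over the level t-test runs from about 2 points (r = 0.3) to 15 points (r = 0.7) at 24 v 24, and from about 2 to 26 points at 12 v 12. Against the change t-test at 24 v 24 it is about 16, 8 and 2 points. Under reading B, the gain over the change t-test at 24 v 24 is about 12, 9 and 5 points. These figures rest on the assumed correlations, two-sided 0.05 and a common SD; the 12 v 12 figures also assume that all 24 enrolled supply both samples.

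Naming the response is worth doing whatever the correlation, because the decision depends on one p-value.

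**What to change.** In 6.2, replace the t-test sentence for the biomarkers. For each marker, the response is the 6-week level, analysed by ANCOVA on the baseline level, the vitamin D factor and the PUFA factor. Test the relevant factor at two-sided 0.05 and report the adjusted difference with its 95% CI.

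Do not require sex and race/ethnicity in the main model at about 24 participants; a pre-specified sensitivity analysis can include them.

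If the biomarker data have already been analysed, keep the planned t-test, state which response it used, and report the ANCOVA beside it as a labelled sensitivity analysis.

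The cost is a short text change and two degrees of freedom relative to the t-test. No new samples are needed. If the change comes after termination, add a sentence saying when and why it was made.
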